6.0 Adverse and Problem Event Reporting

6.1. Responsibilities

It is the responsibility of the principal investigator to notify the IND sponsor of the vaccine research product, [name]., Hopkins Medicine Institutional Review Board, and Hopkins Institutional Biosafety Committee of any serious adverse event due to any cause, which occurs during the course of this investigation, and is believed to be in any way related to study drug. The sponsor will notify the appropriate federal regulatory agencies, including but not limited to the Food and Drug Administration.

The Principal Investigator or their designee must notify the IND sponsor, [name]. of any Serious Adverse Event (SAE) within 24 hours of the investigator learning that the adverse event has occurred. Events must be documented on the appropriate Johns Hopkins Medicine IRB form available at [REDACTED] See section 6.3 for IRB reporting guidelines.

All adverse and problem events occurring from day 0 to 28 of each vaccine cycle will be recorded. All serious adverse and problem events occurring from day 0 and 28 of each vaccine cycle will be reported to the IRB. All serious adverse events related to the vaccine and deaths will be recorded and reported to the IRB. Adverse events related to the vaccine will be followed to resolution.

Events of interest, including but not limited to, vaccine site flares and urticaria, may occur beyond 28 days after the vaccine administration. Immunologic events, such as vaccine site flares and urticaria will be recorded regardless of when they occur. These immunologic events are not to be considered adverse events, since these reactions may represent desired effects from the research product. There are no time restrictions on recording these events, as these events have been known to happen a long time after vaccination.

A *serious adverse event (SAE)* is one that:

- Results in death
- Is life threatening
- Requires inpatient hospitalization or prolongation of an existing hospitalization
- Results in persistent or significant disability/incapacity
- Is a congenital anomaly/birth defect in the offspring of an exposed patient

An important medical event that may not result in death, be life-threatening, or require hospitalization, may be considered a serious adverse drug experience when, based upon appropriate medical judgment, it jeopardizes the subject and may require medical or surgical intervention to prevent one of the outcomes listed in this definition.

A *life threatening adverse event* is defined as any adverse experience that places the patient or subject, in the view of the investigator, at immediate risk of death from the reaction as it occurred, i.e., it does not include a reaction that, had it occurred in a more severe form, might have caused death.

An *adverse drug reaction (ADR)* is a noxious and unintended response to a medicinal product in which a causal relationship between a medicinal product and an adverse event is at least a reasonable possibility, i.e. that the relationship cannot be ruled out.

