Research participants must meet the following criteria.

1. Received the last lethally irradiated GM-CSF transfected allogeneic pancreatic cell lines Panc 10.05 and Panc 6.03 at least 12 months prior (+/- 30 days).
2. Have an Eastern Cooperative Oncology Group (ECOG) performance status of 0 or 1.
3. Have adequate hematologic function (Hemoglobin \geq 9 gm/dl, ANC \geq 1500,/cu mm, platelets \geq 100,000/cu mm)
4. Have adequate renal function (Serum creatinine \leq 2 mg/dl).
5. Have adequate hepatic function (Bilirubin \leq 2.0 mg/dl, unless known Gilbert's Syndrome; AST, ALT and amylase \leq 2x upper limit of normal: Alk Phos \leq 5x upper limit of normal.)
6. Agree to use adequate birth control, if of childbearing potential.

[figure not shown]
[figure not shown]
3.2.5 Exclusion Criteria for Boost Vaccination:

[figure not shown]
Patients with any of the following will be excluded from study entry or will not be able to continue:

1. Radiographical evidence of pancreatic cancer disease recurrence.
2. Documented history of autoimmune diseases including systemic lupus erythematosus, sarcoidosis, rheumatoid arthritis, glomerulonephritis, or vasculitis.
3. Uncontrolled medical problems.
4. Systemic steroid therapy within 28 days before vaccine administration (except for short-term steroid therapy ending at least two days prior to vaccine administration).
5. Anticipated need for systemic steroid therapy within 28 days after vaccine administration.
6. Evidence of active infections.
7. Pregnant.

[figure not shown]

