Data and samples may be obtained from Day-28 to Day 0

1. A clinical evaluation to include vital signs, ECOG status, weight, review of systems, physical examination, and toxicity evaluation.

2. CT scans of the abdomen, pelvis, and chest. If the CT scan is not done at Hopkins, the research participant must provide the report and a copy of the scans. If the research participant is allergic to the CT scan contrast or is contraindicated, a non-contrast CT of the chest and a MRI of the abdomen and pelvis will be obtained.
3. A leukapheresis for in vitro studies will be encouraged. If the research participant refuses a leukapheresis, approximately 200 cc of blood will be drawn. As of Amendment #8, research bloods are no longer required to be collected.
4. Blood testing to include CBC/diff, absolute eosinophils, absolute neutrophils, absolute lymphocytes, comprehensive chemistry panel including electrolytes, albumin, BUN, creatinine, AST, ALT, total bilirubin, and alkaline phosphatase, amylase, and CA 19-9.
5. Research blood: 20 cc for serum banking. As of Amendment #8, research bloods are no longer required to be collected.
6. Pregnancy test for women of childbearing potential. Urine pregnancy test preferred.
7. If not previously enrolled on IRB # NA_00036444 (SKCCC J0248) entitled, Long term follow-up of patients who received lethally irradiated allogeneic pancreatic tumor cells transfected with the GM-CSF gene, the research participant will be encouraged to join the long-term follow-up study.

Day 0

1. Administration of vaccine (Topical lidocaine-based anesthetic may be placed about 1-2 hours prior to planned vaccine administration time to the intended vaccine sites.)
2. Vital signs before and after vaccine administration
3. Photograph of vaccine sites (if clinically indicated)
4. Assessment for toxicities
5. Monitor for 30 minutes after vaccine administration
6. Tetanus toxoid boost if last tetanus vaccination > 10 years. Tetanus/diphtheria (Td) may be substituted if tetanus alone is not available. If both are not available, no tetanus vaccine will be administered.

Day 28 after Boost Vaccine (-3/ + 14 days)

1. A leukapheresis for in vitro studies will be encouraged. If the research participant refuses a leukapheresis, approximately 200 cc of blood will be drawn. As of Amendment #8, research bloods are no longer required to be collected.
2. Assessment for toxicities and vaccine site reactions from previous vaccinations, and medications.

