The risk of generating autoimmune reactions is unknown but is believed to be small. The pancreas would be the most likely organ to be involved. Pancreatitis and loss of pancreatic function can be supported by the use of exogenous pancreatic enzymes and insulin injections if needed. Other organs that may share tissue specific antigens might also be involved, such as the salivary glands and other gastrointestinal organs. In the Phase I and II studies there were no evidence of autoimmune reactions.

Every patient who has received the vaccine will be evaluated for toxicity. The research participant will be taken off-study if unacceptable adverse events are experienced. Possible toxicities include local swelling, induration, or ulceration at the site of the vaccine, systemic toxicities from paracrine secretion of GM-CSF, and induction of autoimmunity. Patients will be evaluated on days 1 and 3 by a research nurse following the semi-annual or annual vaccination boosting to monitor for local and systemic toxicities. The research participant may be contacted by phone or e-mail or the information may be obtained from their local health care providers. The research participant will be advised to call the research nurse and/or the principal investigator if there are any new toxicities, concerns or questions.

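### Section 6.1's 28-day recording window conflicts with 6.2 and 3.4.4 and leaves non-serious autoimmune disease arising later with no assured place in the safety analysis

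*Combined protocol and SAP*

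**What the plan says.** Section 6.1 contains three recording rules:

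- The general rule: "All adverse and problem events occurring from day 0 to 28 of each vaccine cycle will be recorded".
- A rule with no time limit for the gravest events: "All serious adverse events related to the vaccine and deaths will be recorded and reported to the IRB".
- A rule with no time limit for a separate class: "Immunologic events, such as vaccine site flares and urticaria will be recorded regardless of when they occur". This class is then taken out of the adverse-event definition: "These immunologic events are not to be considered adverse events, since these reactions may represent desired effects from the research product".

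Section 6.2 says that every adverse event goes into the case report form and study database with its grade and relationship, and gives no window. Section 3.4.4 sends toxicity data gathered between vaccinations to the same places.

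On autoimmunity, section 3.4.3 lists it among the possible toxicities, names the pancreas, the salivary glands and other gastrointestinal organs, and says: "The risk of generating autoimmune reactions is unknown but is believed to be small". Criterion 2 of section 3.2.5 bars a continuing participant from a boost for this reason: "Documented history of autoimmune diseases including systemic lupus erythematosus, sarcoidosis, rheumatoid arthritis, glomerulonephritis, or vasculitis".

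Section 4.2 makes safety the primary endpoint. It plans a table of toxicities by cohort and vaccination round and, separately, the proportion with a DLT within 28 days of each round.

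**The concern.** The trial gives a cell vaccine repeatedly over years, and safety of the boosts is part of its primary objective. Delayed autoimmunity is a risk that such a design is well placed to describe. The general recording window nevertheless closes at day 28, and it stayed there when Amendment #9 moved boosts from six-monthly to annual.

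Consider a participant who develops rheumatoid arthritis four months after a boost, without hospitalisation. The diagnosis prevents the next boost under criterion 2. The off-study list in section 3.4.6 names serious vaccine-related events but not new autoimmune disease. The site could therefore document an eligibility failure, with no clear instruction to enter a graded adverse event or assign it to a vaccination round. If that happened, the participant would leave the later-round denominators and the event would be missing from the table. That would tilt the by-round tabulation towards safety.

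**Working it through.** The plan gives no figure on this point to reproduce. The check compares the rules and then measures the window.

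**Which rule covers a non-serious autoimmune disease starting in month 4?**

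1. General rule in 6.1: no, because onset is after day 28.
2. Serious-event rule in 6.1: no, unless the investigator uses the discretionary important-medical-event route or finds significant disability, and also judges the event vaccine-related.
3. Immunologic-event rule in 6.1: unclear. The list is open, but its examples are flares and urticaria, and autoimmune disease is not named.
   - If the disease is outside this class, 6.1 has no rule that requires it to be recorded.
   - If it is inside, it is recorded but is declared not to be an adverse event.
4. Section 6.2: yes, if read as unlimited in time. That reading leaves the 6.1 window with no function, so the two sections conflict.
5. Section 3.4.4: interval toxicity data reach the case report form, but the section does not say that they become graded adverse events. The data depend on records requested from outside providers. Once a participant is off study, records are requested for 28 days after the last dose, or longer only to follow related events to resolution.
6. Section 3.4.1, work-up before each boost: "A clinical evaluation to include vital signs, ECOG status, weight, review of systems, physical examination, and toxicity evaluation". This may uncover the disease. No rule says that it is then an adverse event, or to which round it belongs.

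**How much time does the window cover?**

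Inputs: days 0 to 28 inclusive are 29 days (6.1). Boost intervals are 12 months or, formerly, 6 months, each +/- 30 days (3.4.1), taken as 365.25 and 182.6 days.

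Covered share = 29 / interval; uncovered days = interval - 29.

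| Interval | Covered share | Range with +/- 30 days | Uncovered days |
|---|---|---|---|
| Annual | 29/365.25 = 7.9% | 29/395.25 = 7.3% to 29/335.25 = 8.7% | about 336 (306 to 366) |
| Semi-annual | 29/182.6 = 15.9% | 29/212.6 = 13.6% to 29/152.6 = 19.0% | about 154 (124 to 184) |

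Counting 28 days instead gives 28/365 = 7.7% and 28/182 = 15.4%. The move to annual boosts multiplied the uncovered stretch by 336/154 = 2.2.

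The priming doses are 28 days apart (+/- 3 days), so their windows join or nearly join. The gap opens after the third prime and after each boost.

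**The case against.** The strongest reply is that the plan has several ways to catch such an event. Section 6.2 is unrestricted. Section 3.4.4 collects interval records, and for participants followed at the institution these are reviewed at least quarterly, though the stated purpose is disease recurrence. Toxicity is evaluated before every boost and at the off-study visit. Section 6.2 makes worsening to a grade 3-4 laboratory value an adverse event, as well as lower grades judged clinically significant, and amylase is drawn before each boost. Participants are told to call about new toxicities. Long-term follow-up runs in a separate protocol, by consent. All of this stands as evidence of partial capture. None of it settles whether the event is graded and counted as an adverse event of this trial.

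A reader might infer more than the documents support:

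- *That late autoimmune disease would never be recorded.* The routes just listed contradict this.
- *That 84% to 92% of autoimmune events would be lost.* Those are the complements of the covered shares (100 - 15.9 and 100 - 7.9). Reading them as losses assumes uniform onset and no capture by any other route. The plan gives no autoimmune event rate, and section 3.4.3 reports no autoimmune reactions in the Phase I and II studies.
- *That the remark in 6.1, "these events have been known to happen a long time after vaccination", shows late autoimmunity.* It refers to immunologic events such as flares and urticaria.
- *That any pancreatic or salivary event would stop boosts under criterion 2.* The criterion requires a documented autoimmune disease. Rheumatoid arthritis is a named example; new diabetes or mild pancreatitis is not one by itself, and section 2.6 notes that total pancreatectomy causes diabetes.
- *That the DLT estimate is biased.* It is defined on 28 days and is unaffected.

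**Conclusion.** The point holds as an inconsistency and an unfilled classification. Section 6.1 limits general recording to days 0-28, and sections 6.2 and 3.4.4 do not. No section says whether a non-serious autoimmune disease arising later is an adverse event, an exempt immunologic event, or neither. Because autoimmunity is a named toxicity and a documented case ends boosting, a site that follows 6.1 literally can leave such a case out of the by-round tabulation in 4.2.

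The size can be given only as time: about 8% of an annual interval and 15-16% of a semi-annual one lie inside the window. The number of events affected, and hence the bias in the table, cannot be estimated. The conclusion assumes that the case report form, which is not among the documents, does not already settle the matter. It is a modest, inexpensive improvement and does not undermine the 28-day DLT analysis.

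**What to change.** Reconcile 6.1 with 6.2 and 3.4.4:

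- In 6.1, state that new autoimmune disease is recorded and CTCAE-graded as an adverse event whenever it occurs. Cover at least the conditions in criterion 2 of 3.2.5 and autoimmune events in the organs named in 3.4.3. State that the sentence exempting immunologic events does not apply to it.
- Ask about it at the pre-boost and off-study toxicity evaluations already scheduled, and link each case to any boost withheld under criterion 2.
- In 4.2, tabulate these events by time since last vaccine, separately from the 28-day DLT proportion.

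The cost is one paragraph in 6.1, one question at existing visits and one extra table. The downside is that a few more unrelated events will be recorded. Dosing, boost eligibility and the halting rule do not change.

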4.2 Analysis of Primary Endpoint: Safety and toxicity measurements

The primary endpoint of this study is safety as measured by local and systemic toxicity. These toxicities will be characterized according to the National Cancer Institute Common Terminology Criteria for Adverse Events, Version 3.0, and can be accessed and downloaded via the website: <http://ctep.cancer.gov/reporting>. Dermatologic toxicity measurements of the vaccine sites will be performed. For each patient cohort (vaccine naïve and vaccine treated), we will tabulate the number, type and degree of toxicities for each round of vaccination. In addition, we will estimate the proportion of individuals who have a DLT within the first 28 days of vaccination for each round with an exact 95% confidence interval.

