6.2. Recording of an Adverse Event

The principal investigator is responsible for evaluating all adverse events, obtaining supporting documents, and determining that documentation of the event is adequate. The principal investigator is responsible for determining the severity and relationship of the adverse event to the investigational drug. The principal investigator may delegate these duties to sub-investigators and must assure that these sub-investigators are qualified to perform these duties under the supervision of the principal investigator.

All adverse events will be recorded in the subject's Case Report Form and in the study data base. The detailed description of the event will include appropriately graded severity of the adverse event and its relationship to the study drug.

Severity will be categorized by toxicity grade according to the NCI Common Terminology Criteria for Adverse Events version 3.0 available at <http://ctep.cancer.gov/reporting/ctc.html>

Adverse events not listed in the NCI Common Terminology Criteria for Adverse Events will be evaluated using the following criteria:

- Grade 1, Mild: Awareness of symptom, but easily tolerated; usually transient requiring no special treatment; does not interfere with usual status or activities
- Grade 2, Moderate: May be ameliorated by simple therapeutic measures; may interfere with usual activities
- Grade 3, Severe: Incapacitating, inability to perform usual activities
- Grade 4, Life-threatening/Disabling: Subject was at risk of death or significant disability at the time of the event
- Grade 5, Death related to AE

Relationship of the adverse event to the investigational drug will be determined by the principal investigator, and will be categorized as:

- ***Unrelated:*** The adverse event is clearly related to other factors such as the subject's clinical state, environmental factors, or other modes of therapy or concomitant drugs administered to the subject.
- ***Unlikely to be related:*** The adverse event may be related to other factors such as the subject's clinical state, environmental factors, or other modes of therapy or concomitant drugs administered to the subject.

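### Section 6.1 denies adverse-event status to urticaria and vaccine-site flares with no exception for seriousness, so a serious non-fatal case could miss the 24-hour sponsor notice and Section 6.2 grading

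*Combined protocol and SAP*

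**What the plan says.** All references are to the combined protocol and SAP.

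- **Section 6.1, the exclusion.** Immunologic events, with vaccine-site flares and urticaria given as examples, are recorded whatever their time of onset. Then: "These immunologic events are not to be considered adverse events, since these reactions may represent desired effects from the research product". Recording has no time limit because "these events have been known to happen a long time after vaccination".
- **Section 6.1, sponsor notice.** A serious adverse event goes to the IND sponsor "within 24 hours of the investigator learning that the adverse event has occurred". The sponsor informs the federal agencies.
- **Section 6.1, IRB reporting.** Two sentences apply: "All serious adverse and problem events occurring from day 0 and 28 of each vaccine cycle will be reported to the IRB", and "All serious adverse events related to the vaccine and deaths will be recorded and reported to the IRB".
- **Section 6.2.** For each adverse event, "The detailed description of the event will include appropriately graded severity of the adverse event and its relationship to the study drug". Severity follows CTCAE version 3.0.
- **Section 4.2.** "The primary endpoint of this study is safety as measured by local and systemic toxicity". Toxicities are classified by CTCAE version 3.0, vaccine sites are measured, and the number, type and degree of toxicities are tabulated by cohort and vaccination round.
- **Section 3.4.3.** "The research participant will be taken off-study if unacceptable adverse events are experienced". Section 3.4.6 has a similar trigger for serious vaccine-related adverse events.

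**The concern.** Safety is the only primary objective. Section 6.1 first defines a serious adverse event by its outcome (death, threat to life, hospital admission and so on), and the surrounding text attaches duties to that label. The same section then withholds the label from a named class of reactions because they may be a wanted effect. It does not say what happens when such a reaction also meets a seriousness criterion. Urticaria is the clearest case: it is systemic, it is named in the exclusion, and the protocol already gives it enough weight to delay the next vaccination (Section 3.2).

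Two things are at stake. One is expedited notice: if staff follow the sentence as written, a urticaria that leads to hospital admission need not reach the sponsor within 24 hours, and the sponsor's onward notice to the agencies could be late as well. The other is the primary analysis: two analysts could reasonably build different Section 4.2 tables from the same records, one counting urticaria and late flares as toxicities and the other leaving them out as immunologic events.

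**Working it through.** No arithmetic applies. The check is to list what depends on the adverse-event label and then see which other provisions would catch a serious, non-fatal urticaria or late flare.

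**What depends on the label**

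| Duty | Section | Worded for |
|---|---|---|
| 24-hour notice to sponsor | 6.1 | serious adverse events |
| Severity grade and relationship to vaccine | 6.2 | adverse events |
| Follow-up to resolution | 6.1 | vaccine-related adverse events |
| Two off-study triggers | 3.4.3, 3.4.6 | adverse events |

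Section 6.1 removes the label without exception, so on the wording none of these duties is triggered.

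**What could catch the event anyway**

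1. *Recording (6.1).* It applies at any time. It secures a record, but not a grade, an attribution or a deadline.
2. *Serious problem events (6.1).* These do not need the adverse-event label. They go to the IRB, not the sponsor, and only for days 0 to 28 of a cycle.
3. *The IRB sentence without a time limit (6.1).* It covers deaths, whatever the label, and serious adverse events related to the vaccine. A non-fatal event still needs the label.
4. *The important-medical-event clause (6.1).* It rests on medical judgment and does not mention the exclusion.
5. *Section 6.3.* It refers to current IRB and FDA guidelines for problems, events, adverse events and adverse drug reactions. It is general and does not say that it prevails over the exclusion. Section 6.1 defines an adverse drug reaction as noxious and unintended, which sits badly with a reaction described as possibly desired.
6. *Section 7.0.* The sponsor monitors the protocol regularly, so it can learn of a recorded event, but no deadline applies. DSMC oversight draws on monitoring reports and IRB submissions and asks for no additional reporting from study staff.
7. *Section 4.2 and Table 3.* Site measurements and scheduled toxicity and site assessments cover acute local reactions, with assessment continued to resolution. Neither names urticaria or late flares.
8. *Sections 3.1 and 3.4.5.* Continuation of vaccination is worded in terms of toxicities, while the triggers in 3.4.3 and 3.4.6 use adverse events. These passages need to be reconciled with 6.1; no view is taken on what the clinical rule should be.

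**Result by type of event**

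- Acute site reaction: assessed at scheduled visits and probably tabulated under 4.2.
- Death: reported, whatever the label or timing.
- Serious non-fatal urticaria or flare, days 0 to 28: recorded, and goes to the IRB if treated as a problem event; 24-hour sponsor notice and 6.2 grading not assured.
- The same event after day 28: recorded; otherwise dependent on judgment, the general reference in 6.3 and routine monitoring.
- Urticaria or late flare of any grade: status in the 4.2 tables not stated.

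**The case against.** The strongest reply is that the exclusion carries its own limit. It rests on the reactions possibly being a desired effect, and a reaction that puts someone in hospital is hard to describe that way. Seriousness is defined by outcome, and Section 6.3 brings in IRB and FDA guidelines for problems and events as well as adverse events, with no 28-day limit. A careful investigator would probably report such a case. Recording expected immune effects as events of interest is also a reasoned sponsor choice.

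Much of this stands. It makes a missed report less likely and confines the gap to what the text requires. It does not remove the gap, because the sentence has no exception and Section 6.3 does not supply one. The guidelines are not part of the documents, so whether they would close the gap cannot be checked here.

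A second reply is that the exclusion concerns only reactions after day 28, since its paragraph opens with those. The sentence just before it covers these events whenever they occur, which weighs against that reading. Even if accepted, it leaves the exclusion in force exactly where the problem-event route to the IRB has ended.

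Some stronger readings should be resisted:

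- *The sponsor would never learn of these events.* They must be recorded, and the sponsor monitors regularly. It is mainly the 24-hour deadline that is at risk.
- *Local reactions drop out of the primary endpoint.* Section 4.2 and Table 3 cover acute site reactions; the doubt is about urticaria and late flares.
- *Nothing is reported after day 28.* Deaths are.
- *The share of a boost interval lying beyond day 28 measures the gap.* That counts calendar time, not missed events, and ignores the priming phase, where doses are about 28 days apart.

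**Conclusion.** The point holds as a defect of wording with a safety consequence. Read literally, Section 6.1 could leave a serious non-fatal urticaria or late flare without the 24-hour sponsor notice and without the grade and attribution of Section 6.2. It also leaves open whether urticaria and late flares count in the primary toxicity tables.

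The number of events affected cannot be computed: the available text gives no rate for urticaria or flares. Section 2.7.1 describes earlier vaccine-site reactions and rashes as grade 1-2, so serious cases are likely to be few. A reader might infer that the interim toxicity rule in Section 4.1 would undercount. The available text does not show how a dose-limiting toxicity is defined, so no conclusion is drawn on that.

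The conclusion assumes that staff follow the sentence as written and that the guidelines cited in Section 6.3 are not taken to override it. It should be fixed, with medium confidence, because a single sentence decides both an expedited-reporting duty and part of the primary endpoint.

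**What to change.** Replace the excluding sentence in Section 6.1 with wording to this effect:

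> Vaccine-site flares and urticaria are recorded whenever they occur, graded by CTCAE version 3.0, assessed for relationship to the vaccine, and included in the toxicity tables of Section 4.2. Any that meets a seriousness criterion is reported as a serious adverse event, including after day 28. These events may also be analysed as immune markers.

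Add a matching line to Section 4.2 stating that urticaria and late flares are included and how an event with late onset is assigned to a vaccination round.

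The sponsor keeps the immune-marker analysis. The cost is a protocol amendment, some extra event forms, and a toxicity table that may look less favourable.
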